9. STATISTICAL CONSIDERATIONS

9.1 General Design Issues

This study is a randomized controlled trial (RCT) with a waitlist control group with a crossover design. This is a relatively rigorous design for this stage of investigation. Double blinding is not possible in this study, as the participants will know whether or not they are attending the yoga classes. The waitlist intervention will control for time, attention during assessment visits, and the cyclical nature of depression for this early stage investigation.

Hypotheses are clearly outlined in section 9.6 below. Primary and secondary outcome measures are outlined in sections 9.5.1 and 9.5.2 below.

9.2 Sample Size and Randomization

Sample Size and Power Estimation: Although this study will test for statistical significance, the primary aim of this pilot RCT is to estimate the intervention's effect size to conduct a more definitive R01 study, as is outlined in NIH guidelines for developing behavioral interventions³³. The study was powered conservatively based on an 80% (n=64) ITT sample. Effect sizes for the degree of change in IDS-CR (primary outcome) were estimated for the hyperthermic yoga versus the control using Cohen's d (effect size for t-test). A power analysis found that with an ITT sample of 64 (32 per arm), a two-tailed t-test with an alpha level of .05 will yield a statistical power of 79% to detect a large effect size of .70 and 50% to detect a moderate effect size (.50). Thus, if the effect size falls between moderate and large, power would approach 80%, since the evaluable sample should be between 64 and 80. Preliminary data suggested a moderate effect size of .54 for depression³⁴. We predict a more robust effect size of at least .60-.70, as this is a larger sample recruited specifically for depressive symptoms.

Randomization: Our biostatistician will establish the blind and deliver it to the designated Research Coordinator. Randomization will be done by random permuted block design in blocks of 2 and 4. This method assigns subjects to each intervention group with equal probability, while at the same time generating a balanced design. The random permuted block randomization method also protects against bias due to temporal trends (e.g., experience of research staff, or seasonal effect). This randomization design should balance the heterogeneity of the subjects between groups.

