Bikram Yoga Research: While there is no literature on Bikram Yoga for depression, several studies of Bikram Yoga demonstrate improvements in physiological and psychological processes implicated in depression. **Physiologically:** In a recent 8-week pilot trial, 3 weekly

Bikram Yoga classes improved glucose tolerance in 15 older obese adults compared to 14 young lean subjects. This supports Bikram Yoga as a therapeutic tool for metabolic dysfunction²⁹, and depression is associated with metabolic disorders³⁰. Another study found that 8 weeks of 3 weekly Bikram Yoga classes improved arterial stiffness in 24 younger adults (30±1 years), and significantly reduced insulin resistance in 18 older adults (53±2 years)³¹. The relationship between depressive and anxiety disorders and early markers of arterial stiffness³², indicates a common pathophysiology with depression. **Psychologically:** In an uncontrolled study of 54 healthy individuals, Bikram Yoga improved mindfulness and decreased stress³³, suggesting benefits in depression via effects on mindfulness and perceived stress. In an unpublished dissertation, DeBoer et al.³⁴ reported preliminary completer data of twice weekly Bikram Yoga classes (n=27) versus a waitlist control (n=25) for women (ages 25-45) with stress-induced eating and high perceived stress. This study demonstrated a dropout rate of 11.5%, lower than in most depression trials. The 4 subjects who discontinued yoga did so in the initial stages of the practice. This study provided preliminary evidence of the acceptability of recruiting and retaining a psychiatric population for this intervention. The effect size for the change in the Beck Depression Inventory (BDI-II)³⁵, based on Cohen's *d*, was medium (0.54), suggesting an advantage for Bikram Yoga over the waitlist. As this study did not require depressive symptoms for entry, the effect size for depression in the proposed study will likely be higher. The Beck Anxiety Inventory (BAI)³⁶ demonstrated a large effect for Bikram Yoga over control (*d*=1.19). There were also large effects for Bikram Yoga's ability to reduce scores on the Ruminative Responses Scale (RRS)³⁷ (.76), the Perceived Stress Scale (PSS)³⁸ (.83), and the Response to Positive Affect Scale³⁹ (.76). I will include the PSS and RRS in our study as secondary outcome measures, due to these results.

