Primary Aim II: To collect the Inventory of Depressive Symptomatology – Clinician Rated (IDS-CR) scores at screening; baseline; and weeks-1, -3, -5 and -8 to evaluate the efficacy of hyperthermic yoga for depressive symptoms.

Hypothesis II: The IYG will have greater decreases in Inventory of Depressive Symptomatology – Clinician Rated (IDS-CR) scores after 8-weeks compared to the DYG.

Response over 8-weeks defined by 50% or greater decrease on IDS-CR total; remission ≤ 11 on IDS-CR total. Continuous variables will be analyzed by generalized mixed effect modeling, which impute missing values based on maximum likelihood estimates of missing parameters, allowing analysis of all MITT participants. A time-by-condition interaction will be analyzed to test the intervention's efficacy. Relevant potential covariates (e.g., attendance) will also be examined.

Primary Aim III: To collect (a) physiological and (b) psychological mediators of hyperthermic yoga in the IYG and DYG group at screening; baseline; weeks-1, -3, -5 and -8 to evaluate treatment response in the IYG compared to the DYG.

Hypothesis IIIa: Salivary cortisol, and inflammatory markers (i.e., Tumor Necrosis Factor [TNF- α], Interleukin-6 [IL-6], and C-Reactive Protein [CRP]) will significantly decrease, following 5- and 8-weeks of hyperthermic yoga in the IYG compared to the DYG.

Hypothesis IIIb: Perceived stress, mindfulness, and rumination will improve by 5- and 8-weeks in the IYG compared to the DYG.

Latent growth curve modeling will assess potential mechanisms of the treatment effect. The slope (change over time) of the mediator variables will be regressed upon the independent variable (condition). The slope of the dependent variable will also be regressed upon the slope of the mediators. This model will permit assessment of the change in mechanisms as it predicts the change in the dependent variables.

Secondary Aim I: To collect measures of quality of life, general health, physical functioning, decreased perceived stress, anxiety, and sleep in the IYG and DYG at screening; baseline; and weeks-1, -3, -5 and -8 to evaluate hyperthermic yoga for secondary outcome measures.

Secondary Hypothesis I: The IYG will have significant improvements in quality of life, general health, physical functioning, perceived stress, anxiety, and sleep compared to the DYG.

These will be analyzed by the same methods as outlined for Primary Aim II (above).

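### Section 9.2 overstates power: between d = .50 and .70 with 64 to 80 evaluable, its own t-test gives 50% to 87%, and only 57–66% at the preliminary effect of .54

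*Combined protocol and SAP*

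**What the plan says.** Section 9.2 bases the power statement on IDS-CR change, with Cohen's d as effect measure and "a two-tailed t-test with an alpha level of .05". It takes 80% of the 80 randomised as its working sample, which is 64, or 32 per arm. It states that this sample "will yield a statistical power of 79% to detect a large effect size of .70 and 50% to detect a moderate effect size (.50").

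The conclusion follows directly: "if the effect size falls between moderate and large, power would approach 80%, since the evaluable sample should be between 64 and 80". The paragraph's own labels make moderate .50 and large .70.

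The next two sentences cite a preliminary effect of .54 and predict at least .60–.70, "as this is a larger sample recruited specifically for depressive symptoms". No power is given for .54 or .60, and none for 80 evaluable.

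The section also says that, although significance will be tested, the pilot's primary aim is to estimate the effect size. Section 9.6 plans a mixed model for the efficacy test: "A time-by-condition interaction will be analyzed to test the intervention's efficacy".

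**The concern.** The plan gives power at the two ends of an effect-size range and then makes a statement about everything between them. At the lower end its own figure is 50%, which is far from 80%. The reason offered, that between 64 and 80 will be evaluable, would have to close that gap, so it can be checked directly.

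The effect sizes discussed next (.54 and .60) lie in the lower half of the range. For those values the general sentence is all the reader has. Hypothesis II in section 1.1 is an efficacy hypothesis under a primary aim, and section 9.4 says the full sample is needed to assess efficacy. If the result is not significant, a reader who believes power was close to 80% may take it as evidence against an effect of .54 to .60. The planning test gives much weaker grounds for that.

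There is also a smaller point of reasoning. The paragraph supports a higher predicted d partly by the size of the sample. A larger sample narrows the interval around d and raises power; it does not make the true d larger.

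**Working it through.** **Inputs**
- Test: two-sample t-test, two-sided, alpha .05 (section 9.2).
- Evaluable sample: 64 to 80 (section 9.2), 1:1, so n = 32 to 40 per arm (section 1.1 randomises 40 per arm).
- Effect sizes: .50 and .70 (the plan's moderate and large), .54 (preliminary) and .60–.70 (predicted), all from section 9.2. The value .65 is the midpoint of the prediction.

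**Formula.** With n per arm, the t statistic follows a non-central t distribution with 2n − 2 degrees of freedom and non-centrality d × √(n/2). Power is the probability that |t| exceeds the two-sided 5% critical value.
- n = 32: 62 degrees of freedom, critical value 1.999, non-centrality d × √16 = 4d.
- n = 40: 78 degrees of freedom, critical value 1.991, non-centrality d × √20 = 4.472d.

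**Step 1: reproduce the plan's figures (n = 32).**
- d = .70: non-centrality 2.80, power 78.7% (plan: 79%).
- d = .50: non-centrality 2.00, power 50.4% (plan: 50%).

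Both agree. A one-sided test would give 87% and 63%, so the two-sided t-test is the plan's method.

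**Step 2: the same test across the stated range.**

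| d | Power, 64 evaluable | Power, 80 evaluable |
|---|---|---|
| .50 | 50.4% | 59.8% |
| .54 | 56.6% | 66.5% |
| .60 | 65.6% | 75.5% |
| .65 | 72.6% | 81.9% |
| .70 | 78.7% | 87.1% |

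**Step 3: effect size needed for 80% power.** Solving the same formula for d gives .711 with 64 evaluable and .634 with 80. With 64, power is below 80% at every d from .50 to .70.

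**Step 4: sample needed for 80% power.**

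| d | n per arm | Total evaluable |
|---|---|---|
| .54 | 55 | 110 |
| .60 | 45 | 90 |
| .65 | 39 | 78 |
| .70 | 34 | 68 |

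The totals at .54 and .60 exceed the 80 to be randomised.

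**Step 5: chance of missing a true effect of .60.** 1 − .656 = .344 with 64 evaluable, and 1 − .755 = .245 with 80. That is about one trial in three to one in four.

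**Step 6: precision of the estimate.** Inverting the non-central t for observed d of .50 to .70 gives a 95% confidence interval half-width for d of .498–.505 with 32 per arm and .445–.452 with 40 per arm, so about 0.50 and 0.45.

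**The case against.** The case for leaving the sentence alone is that it contains no false number. Both computed figures are right, and the 50% at d = .50 stands just before the conclusion, so a careful reader is warned. The word approach is loose: at .65, the middle of the prediction, power is 73–82%, which fits it, and at .70 it is 79–87%. The plan presents .60 as the floor of its prediction, and .54 lies below that floor. The study is a pilot whose stated main aim is estimation. Efficacy will be tested by a mixed model on repeated IDS-CR scores, so the t-test powers describe the planning calculation and not the final test.

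Much of this stands, and it limits the weight of the point. The upper part of the range is adequately powered, estimation is not affected, and the mixed model may do better or worse; the documents give no within-person correlation from which to compute its power.

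It does not rescue the sentence. The claim covers the whole interval from moderate to large. Even with no loss at all, power is 60% at .50 and 66% at .54, and neither approaches 80%. At .60 it reaches 76% only if every randomised participant is evaluable. Giving 50% at one end does not tell the reader the power at .54 or .60.

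On the predicted effect, the second reason, recruiting people with depressive symptoms, is substantive. Section 2.2 makes the same argument: "As this study did not require depressive symptoms for entry, the effect size for depression in the proposed study will likely be higher". Only the sample-size half of the justification fails.

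**Conclusion.** The concern holds. The conclusion on power in section 9.2 is wrong as written for the lower part of its stated range. By the plan's own test, power over d = .50 to .70 and 64 to 80 evaluable runs from 50% to 87%. It is 57–66% at .54 and 66–76% at .60, and it reaches 80% only from d of about .63 (all 80 evaluable) or .71 (64 evaluable).

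This rests on the plan's inputs: a two-sided t-test, alpha .05, equal arms and 64 to 80 evaluable. It does not extend to the mixed-model interaction test. If instead only 60 were evaluable (an assumption: the 75% retention target in section 1.1 applied to 80), the t-test power would be lower still: 54% at .54, 63% at .60 and 76% at .70. Under the modified ITT definition in section 9.3, participants who leave after one post-baseline visit still count, so 60 may be pessimistic.

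The correction should be made, but it is one of wording. The two stated powers are correct, and neither the design nor the estimation aim is undermined.

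**What to change.** In section 9.2, replace the concluding sentence on power with text such as:

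> Using the same two-sided t-test at alpha .05, 64 to 80 evaluable participants give power of 50–60% at d = .50, 57–66% at .54, 66–76% at .60, 73–82% at .65 and 79–87% at .70. Power of 80% requires d of about .71 with 64 evaluable or .63 with 80. These figures apply to the t-test; the planned mixed model may differ.

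In the sentence predicting the effect size, remove sample size as a reason and keep only the recruitment of people with depressive symptoms.

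Optionally, since estimation is the stated primary aim, add that the expected 95% confidence interval half-width for d is about 0.50 with 64 evaluable and 0.45 with 80.

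The cost is a small text change and a less favourable power statement. No participants, visits or analyses are added or altered.

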9.3 Definition of Populations

A completer will be defined as a subject who attends: 1) a screen, 2) baseline, 3) at least one midpoint assessment (week-1, -3, or -5), and 4) a week-8 assessment visit. We will complete two analyses: 1) a completer analysis and 2) a modified ITT (MITT) analysis. The MITT will include those who have attended at least one post-baseline assessment visit. Our primary analyses utilize data from the IYG and DYG prior to the crossover.

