1. STUDY OBJECTIVES

1.1 Primary Objective

Primary Aim I: To recruit and retain adults with depressive symptoms into a controlled trial of hyperthermic yoga, randomizing 40 participants to each the immediate yoga group (IYG) and delayed yoga group (DYG; control group) with seventy-five percent retention in both groups.

Hypothesis 1a: Seventy-five percent of the each group will complete a week-8 assessment.

Hypothesis 1b: Acceptability of hyperthermic yoga will be high on the Acceptability Interview.

Primary Aim II: To collect the Inventory of Depressive Symptomatology – Clinician Rated (IDS-CR) scores at screening; baseline; and weeks-1, -3, -5 and -8 to evaluate the efficacy of hyperthermic yoga for depressive symptoms.

Hypothesis II: The IYG will have greater decreases in Inventory of Depressive Symptomatology – Clinician Rated (IDS-CR) scores after 8-weeks compared to the DYG.

Primary Aim III: To collect (a) physiological and (b) psychological mediators of hyperthermic yoga in the IYG and DYG group at screening; baseline; weeks-1, -3, -5 and -8 to evaluate treatment response in the IYG compared to the DYG.

Hypothesis IIIa: Salivary cortisol, and inflammatory markers (i.e., Tumor Necrosis Factor [TNF- α], Interleukin-6 [IL-6], and C-Reactive Protein [CRP]) will significantly decrease following 5- and 8-weeks of hyperthermic yoga in the IYG compared to the DYG.

Hypothesis IIIb: Perceived stress, mindfulness, and rumination will improve by 5- and 8-weeks in the IYG compared to the DYG.

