Bikram Yoga focuses almost exclusively on the physicality of the practice, rather than the spiritual components of yoga.	Yoga modalities range in degree of physical and/or spiritual emphasis ²⁷ . The physical focus may have broader, secular-based appeal to US public.
Widely Available: 285 Bikram Yoga studios in the US and 217 Bikram Yoga studios abroad, covering 42 countries and 464 cities; 18 Bikram Yoga studios in Massachusetts.	The intervention has broad potential for quick dissemination.

Yoga as a Treatment for Depression: Evidence is accumulating to support yoga as a treatment for depression. A 2005 literature review found 5 randomized controlled trials (RCTs)¹¹, whereas a 2013 meta-analysis found 12 RCTs¹². Reviews suggest that yoga is a promising treatment for depression, but consistently note that a lack of rigorous study methodology prevents the firm conclusion that yoga be considered a treatment for depression^{9, 12, 28}. Methodological limitations include: heterogeneity of yoga interventions and patient samples; inadequate sample size and randomization procedures; lack of intention-to-treat analysis and blinding of outcome assessors; inadequate control groups; and unreported dropout, relapse, and remission rates^{9, 12}. Despite these flaws, the 2013 meta-analysis¹² did find moderate evidence for the short-term effects of yoga compared to usual care. A 2013 systematic review of yoga for depression¹⁰ affirmed “Grade B” evidence for yoga as an acute treatment for depression. One controlled study used an Iyengar yoga treatment, a form of hatha yoga, that included back bends, inversions and vigorous standing postures thought to be particularly effective for alleviating depression⁸. These postures are also used in Bikram Yoga, which is also a form of hatha yoga. The Beck Depression Inventory (BDI) and Spielberger State-Trait Anxiety Index (STAI) measured mood and anxiety. Subjects had baseline BDI scores of 10 to 15 (mild-to-moderate depressive symptoms), similar to the proposed study. The 5-week yoga intervention decreased depression and anxiety, using similar measures to the proposed study. The evidence has been promising enough to warrant two current rigorous NIH R01 funded RCTs for non-heated yoga (NIH RePORTER: 1) PI: [name] [NCCAM], and 2) PI: Uebelacker [NINR]). The proposed study has been constructed to address the concerns and apply rigorous methodology to an unexplored form of yoga.

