3. STUDY DESIGN

The project is an acceptability, feasibility, and pilot efficacy trial of hyperthermic yoga vs. a waitlist control for 80 adults with at least mild depressive symptoms. The target enrollment for the study will be 160 to properly screen the number of needed randomized participants. The hyperthermic yoga intervention will take place in two community Bikram Yoga studios in the Boston area. Bikram Yoga Boston is owned by [name] and Bikram Yoga Cambridge is owned by [name]. Participants will attend classes at either of these studios, free of charge – i.e., the intervention will be community-delivered. Participants will be asked to attend

at least two weekly 90-minute Bikram Yoga classes during the 8-week intervention phase of the study. All research related assessments will take place at the Depression Clinical and Research Program (DCRP) at the Massachusetts General Hospital (MGH). The enrollment period for participants will depend upon the arm to which they are randomized: 1) immediate yoga group (IYG) will complete the protocol in approximately 15 weeks; and 2) the control or delayed yoga group (DYG) will complete the protocol in approximately 24 weeks.

Retention Strategies: Patients with depressive symptoms frequently have impaired motivation. In the only known RCT of hyperthermic yoga for a psychiatric population, subjects who dropped out tended to do so after 1-2 sessions. Most who got through this critical period completed the study³⁴. To address this: 1) study staff, the PI or designee, will administer a 50-minute pre-yoga baseline psychoeducation session with a preparatory handout, which they take home with them. 2) Participants will receive a bi-weekly telephone call from the PI, and when not available, another study staff member.

Subject Remuneration: Subjects in the DYG will be compensated for their time during the waitlist period (\$25 for baseline; week 1, 3, 5 and 8; total=\$125) to encourage participation. Subjects in IYG will only be paid for the 1-month follow up visit (\$25), as they will receive free yoga classes at the outset of the study. All subjects will receive \$30 per cortisol assessment.

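### No efficacy analysis includes all randomised participants: the MITT drops those who never return after learning their arm, which can bias the effect size meant for the R01 in a direction the documents do not settle.

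*Combined protocol and SAP*

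**What the plan says.** Section 9.3 (Definition of Populations) plans two sets and no more: "We will complete two analyses: 1) a completer analysis and 2) a modified ITT (MITT) analysis". For the second, "The MITT will include those who have attended at least one post-baseline assessment visit". Completers must also attend a midpoint visit and week 8, so that set lies inside the MITT. Section 9.6 fits the mixed model for Primary Aim II to MITT participants.

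Other sections bear on this:

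- Section 9.2 labels the set used for power as ITT: "The study was powered conservatively based on an 80% (n=64) ITT sample". It also states that "the primary aim of this pilot RCT is to estimate the intervention's effect size to conduct a more definitive R01 study".
- Section 2.2 names "lack of intention-to-treat analysis and blinding of outcome assessors" among the weaknesses of earlier yoga trials and presents this study as built to address such weaknesses.
- Section 6.2.2 has participants told their arm when the baseline visit ends, after all baseline measures.
- Section 3 pays the DYG $25 at baseline and at weeks 1, 3, 5 and 8. The IYG gets $25 at the one-month follow-up only, because its classes are free from the start. Both arms get $30 per cortisol assessment.
- Section 8 says participants taken off the intervention, including anyone with no yoga for two weeks, will be in the MITT and invited to Visit 6. For the definition it points to section 9.

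**The concern.** Membership of the main analysis set is decided by something that happens after randomisation, and after the participant knows the arm. Once analysis depends on coming back, the two groups compared are no longer the two groups randomised.

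The reasons for coming back differ by arm. IYG participants face a demanding intervention and no visit payment at weeks 1 and 3. DYG participants face a wait and are paid. Before the crossover, the two-week no-yoga rule in section 8 can apply only to the IYG. Disappointment at being put on a waitlist could act in the other direction.

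What is at stake is the number the pilot exists to produce. If the non-returners differ from those retained, and the arms lose different shares, the estimated d is not the effect of offering the intervention. An R01 sized on it could be too small or too large. Nothing in the plan would show the size of the problem, because no analysis of all randomised participants is described and the method for data not missing at random is left unnamed in section 9.6.

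**Working it through.** **The plan's own figures.** 80% of 80 is 64, or 32 per arm. A two-sided two-sample t-test at alpha .05 with 32 per arm (noncentral t) has 78.7% power at d = .70 and 50.4% at d = .50. Section 9.2 states 79% and 50%, so the power statement reproduces. Only its ITT label disagrees with section 9.3: an ITT set here is 80, not 64.

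**Payment by visit, DYG against IYG** (section 3, with the cortisol visits from the schedules in 6.1.1 and 6.1.2):

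- Weeks 1 and 3: $25 against $0.
- Weeks 5 and 8: $25 + $30 = $55 against $30.

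**Who is excluded.** Anyone randomised with no assessment after baseline. Someone who stops yoga but attends any one of weeks 1, 3, 5 or 8 stays in. Section 8 would keep every discontinued participant, whereas section 9.3 drops those with no later visit; the two disagree for exactly this group.

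**Illustration.** The documents give no share f of the IYG who never return, so f is an assumption. Assume also that these people gain nothing (outcome like the control mean), that the DYG loses nobody, and that the SD is unchanged. Then

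d(all randomised) = d(MITT) × (1 − f).

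For 80% power, n per arm = 2(1.960 + 0.842)² / d² = 15.70 / d². At d = .60 this is 43.6.

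| f | People of 40 | d, all randomised | n per arm needed | Increase over 43.6 | Shortfall of needed n |
|---|---|---|---|---|---|
| 5% | 2 | .57 | 48.3 | 11% | 10% |
| 10% | 4 | .54 | 53.8 | 23% | 19% |
| 15% | 6 | .51 | 60.4 | 38% | 28% |

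The last two columns use different bases: 60.4 / 43.6 = 1.38, but 1 − 43.6 / 60.4 = 0.28. With the t-test in place of the normal approximation, the R01 would be planned at 45 per arm and would need 50, 55 or 62. Its power at 45 would be 76%, 72% or 67%.

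**General form.** If non-returners do k SD worse than those retained in both arms, each arm's MITT mean is too favourable by k times its own loss, so

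bias in d = k × (f_IYG − f_DYG).

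With k = .5:

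- Losses of 20% and 5% give .5 × .15 = +.075.
- Equal losses give 0.
- Losses of 5% and 20% give −.075.

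The table above is the special case k = .60 and f_DYG = 0.

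**The case against.** A reader might infer more from section 3, which reports of a prior trial that "subjects who dropped out tended to do so after 1-2 sessions": that people who try yoga once or twice and leave are removed from the analysis, that these removals fall in the IYG, and that the R01 would therefore be undersized. The documents do not support that. The quoted pattern concerns leaving yoga, while section 9.3 turns on assessment visits. At two classes a week, one or two sessions is about week 1, when Visit 3 falls, and three further visits follow before the week-8 endpoint is closed. Section 8 invites those who stop to Visit 6, section 6.2.5 makes Visit 6 the early discontinuation visit, and section 6.2.4 allows clinician ratings by phone. Section 3 also describes countermeasures: a preparatory session and regular calls.

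Three more points stand:

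- The prior trial's 11.5% in section 2.2 is its overall dropout rate, so 15% never returning exceeds the only dropout rate cited from an earlier trial.
- With 32 to 40 per arm, the standard error of d near .60 is about .26 to .23, so shifts of .03 to .09 are small beside the pilot's own imprecision.
- Putting baseline-only participants into a likelihood-based mixed model hardly moves the estimate under missing at random, because they carry almost no information on the week-8 contrast.

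What does not stand is the defence that maximum likelihood already deals with the matter. As planned, it operates within the MITT and never sees the non-returners. Imprecision is no defence either: a systematic shift adds to random error.

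**Conclusion.** The gap is real and narrow. Participants who never return after baseline are in no efficacy analysis, although their arm has been disclosed and the payments to return differ. The resulting bias in d can be positive, zero or negative, depending on losses in both arms that the documents do not give. Inflation is plausible if the IYG loses more non-responders, but it is not established.

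Under the stated assumptions (5% to 15% of the IYG never return and gain nothing, no DYG loss), an MITT d of .60 stands for .57 to .51 in all randomised participants, and an R01 sized on .60 would need about 11% to 38% more per arm. These figures show sensitivity and are not a forecast. Separately, the ITT label in section 9.2 does not fit section 9.3, and sections 8 and 9.3 contradict each other on discontinued participants with no later visit.

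**What to change.** Before database lock:

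1. In section 9.3, define the primary set as all randomised participants, analysed as assigned, with baseline IDS-CR in the outcome vector of the mixed model. Randomisation follows the baseline measures, so the value is scheduled for everyone. State that under missing at random this step alone will change the estimate little.
2. Add a multiple-imputation sensitivity analysis on all randomised participants, either control-based for missing IYG data or delta-adjusted. Delta adjustment set separately by arm also covers the case in which DYG losses matter more. Report its d beside the primary d for R01 planning. This is the part that can change the conclusion.
3. Report the number of non-returners by arm.
4. Keep the MITT and completer analyses as supportive.
5. Reconcile section 8 with section 9.3, and correct the ITT label in section 9.2.

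The cost is revised wording and one extra analysis, with no new data. The downside is a possibly less favourable effect estimate.
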